10.2 MEASUREMENT OF TREATMENT COMPLIANCE AND TOLERABILITY

In this study, compliance to the insertion and removal procedures outlined in the protocol is assessed by the investigator. This information is collected in the IP insertion and removal eCRFs. The information in these eCRFs will be summarized by treatment group for each treatment period. Furthermore, associated listing will be produced.

For patients that spontaneously abort the IP or ask the IP to be removed prior to the Day 14 post-IP insertion, a summary table of such events will be presented by treatment group and overall.

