5.6.3 Premature IP Removal

The IP will be removed immediately and appropriate medical therapy should be instituted immediately, if any of the following occur:

• if patient requests removal of the IP for any reason

- if patient becomes pregnant
- haematuria that is considered by the investigator to be clinically significant
- urinary retention that is considered by the investigator to be clinically significant
- allergic reaction (shortness of breath, generalized edema, etc) to either LiRIS device constituent materials (silicone, nitinol), drug (lidocaine or lactose) and/or excipients (povidone, polyethylene glycol)
- signs of lidocaine toxicity (Xylocaine[®] Injection Package Insert, 2010) where toxicities associated with lidocaine include but are not limited to light-headedness, nervousness, perioral tingling, tingling or numbness of the tongue, confusion, dizziness, drowsiness, tinnitus, blurred or double vision, vomiting, sensations of heat, cold or numbness, twitching, tremors, convulsions, unconsciousness, respiratory depression, respiratory arrest and cardiovascular reactions which are usually depressant in nature and are characterized by bradycardia, hypotension, and cardiovascular collapse, which may lead to cardiac arrest
- a condition or situation that, in the investigator's opinion, may put the patient at significant risk

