10.0 EXTENT OF EXPOSURE AND TREATMENT COMPLIANCE

In this study patients receive two insertions of IP in Treatment 1 and one insertion of IP in Treatment 2. Treatment 2 is provided if the patient makes a request and qualifies for re-treatment. A request for re-treatment can only be made 4-weeks after the second IP had been removed. Hence, what are relevant in this study would be the duration of each treatment period (Treatment 1 and 2), whether or not the insertion and removal of the IP was completed as per the instruction provided in the protocol and whether or not a patient completed the 14 days cycle for each inserted IP.

10.1 **EXTENT OF EXPOSURE (DURATION OF EFFECT)**

Treatment duration for each Treatment period (1 or 2) will be displayed by treatment groups as well as the cumulative study duration over the entire study period. For Treatment 1 period, the treatment duration could be thought of as duration of effect. The following formula will be used to derive treatment duration:

Cumulative treatment duration:

Cumulative duration = exit date – Date of Treatment 1 first IP insertion + 1

Treatment 1 duration:

exit date – Date of Treatment 1 first IP insertion + 1,

for patients that exit without receiving Treatment 2 or,

Date of Treatment 2 IP insertion - Date of Treatment 1 first IP insertion

Treatment 2 duration:

exit date – Date of Treatment 2 IP insertion + 1,

If the date of exit date is missing, the date of the last visit will be used.

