- If an event occurs during the Treatment 1 period and continues to the Treatment 2 period without increasing in severity, this event will be counted as an event during the Treatment 1 period but will not be counted again as an event in the Treatment 2 period.
- If an event occurs during the Treatment 1 period or earlier and continues to the Treatment 2 period and the severity increases to a grade that is greater than the maximum severity of the Treatment 1 period or the pre-treatment period or becomes serious in Treatment 2 period then the event will be counted as an event in the Treatment 2 period.

For each treatment phase and for the overall treatment period the number and percentage of patients reporting TEAEs in each treatment group will be tabulated by descending percentage in any group, by system organ class and preferred term, and further categorized by severity and causal relationship to the study treatment. If more than 1 AE is coded to the same preferred term for the same patient, the patient will be counted only once for that preferred term using the greatest severity and strictest causality for the summarization by severity and causal relationship. All AE summary tables will be by treatment group and the overall safety population.

The total number of TEAEs by severity and causal relationship to the study treatment will be summarized by treatment group.

The number and percentage of patients who have Treatment emergent SAEs will be summarized by preferred term and treatment group. In addition, the incidence of treatment emergent SAEs that led to death will be summarized separately by preferred term for each treatment group.

The number and percentage of patients in the Safety Population who have AEs leading to premature discontinuation of the study treatment will be summarized by preferred term and treatment.

Pretreatment AEs are the AEs that occur after signing of the informed consent (IC) and prior to first dose of study medication. Such AEs will be presented in a patent listing.

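### The SAP 10.2 early-removal table counts only devices expelled or removed at the patient's request, so removals made solely on the investigator's decision under protocol 5.6.3 are not counted

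*SAP*

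**What the plan says.** Protocol 5.6.3 (Premature IP Removal) opens its list with "The IP will be removed immediately and appropriate medical therapy should be instituted immediately, if any of the following occur". Seven triggers follow. The first is "if patient requests removal of the IP for any reason". The others are pregnancy, "haematuria that is considered by the investigator to be clinically significant", clinically significant urinary retention, allergic reaction, "signs of lidocaine toxicity", and a situation that the investigator judges a significant risk.

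SAP 10.0 says that one of the relevant matters in this study is "whether or not a patient completed the 14 days cycle for each inserted IP". SAP 10.2, whose title covers compliance and tolerability, plans two things. First, the insertion and removal eCRFs will be summarized by arm for each treatment period, with a listing. Second, it plans a dedicated early-removal table. The patients in that table are defined by "For patients that spontaneously abort the IP or ask the IP to be removed prior to the Day 14 post-IP insertion", and for them "a summary table of such events will be presented by treatment group and overall".

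SAP 12.1 separately plans treatment-emergent adverse event tables, a table of lidocaine-toxicity preferred terms, and a table for patients who have "AEs leading to premature discontinuation of the study treatment will be summarized by preferred term and treatment".

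**The concern.** An acceptable safety profile for two consecutive LiRIS 400 mg is part of the study's clinical hypothesis. How often a device had to come out early, and why, is a natural tolerability measure for an indwelling product. The one table that the SAP defines for this is restricted by who prompted the removal, although SAP 10.0 attaches no such condition to completing the cycle. Followed as written, the table leaves out removals that the investigator decided on medical grounds without a request from the patient.

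The layout raises a second issue. The eCRF summary is split by treatment period, but the sentence defining the early-removal table mentions only arm and overall. An arm label does not identify what was in the bladder. Placebo/LiRIS patients have a placebo device and then an active one, and every Treatment 2 device is active.

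**Working it through.** The main check is a comparison of texts. The plan gives no early-removal figure to reproduce.

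**Step 1: triggers against the table definition.**

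| Protocol 5.6.3 trigger | Counted in the SAP 10.2 table? | Where the underlying event could appear |
|---|---|---|
| Patient request | Yes | – |
| Pregnancy | Only if the patient also asks | Pregnancy test listing (SAP 12.5.5) |
| Haematuria | Only if the patient also asks | Adverse event tables (12.1) |
| Urinary retention | Only if the patient also asks | Adverse event tables; post-void residual summary (12.5.1) |
| Allergic reaction | Only if the patient also asks | Adverse event tables |
| Signs of lidocaine toxicity | Only if the patient also asks | Adverse event tables; lidocaine-toxicity table (12.1) |
| Investigator-judged risk | Only if the patient also asks | Adverse event tables, if an event is recorded |

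The table names 1 of 7 triggers, plus expulsion, which is not a 5.6.3 trigger. The other 7 − 1 = 6 lie outside its wording. This counts kinds of reason. It is not a share of removals.

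**Step 2: does another defined output count all early removals?**

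- *Treatment duration (SAP 10.1).* Treatment 1 duration runs from first insertion to exit or to Treatment 2 insertion. Treatment 2 duration runs from its insertion to exit. No formula uses a removal date. Two patients with the same insertion and exit dates have the same duration even if one device came out on day 2 and the other on day 14.
- *Adverse events ending study treatment (SAP 12.1).* This needs an adverse event linked to stopping study treatment. The SAP does not say whether losing one of up to three devices qualifies. Under protocol 9.1.1, worsening attributed unequivocally to disease progression or lack of efficacy is generally not reported as an adverse event, so a removal for that cause could be missed here.
- *Lidocaine-toxicity terms (SAP 12.1).* This counts events, not removals. Its list has no term for haematuria, urinary retention or allergic reaction.
- *Per-protocol count (SAP 6.4 and 7.0).* Membership requires both devices to be retained for 28 days, but also the Week 4 Follow-up visit and no significant deviation. Early removals cannot be read off from it.
- *Reasons for discontinuation (SAP 7.0).* These concern leaving the study, not losing a device.
- *Insertion and removal eCRF summary and listing (SAP 10.2).* These may carry the date and reason of removal. The fields are not in the documents, and SAP 4.0 places table specifications elsewhere.

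None of these is defined as a count of every early removal by cause and device.

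**Step 3: what an arm label covers.** The planned arm sizes are 38, 19 and 19 (protocol 3; SAP 4.0). If every randomized patient receives both Treatment 1 devices:

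- LiRIS/LiRIS: 38 × 2 = 76 active
- Placebo/Placebo: 19 × 2 = 38 placebo
- Placebo/LiRIS: 19 placebo + 19 active = 38

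The totals are 76 + 19 = 95 active and 38 + 19 = 57 placebo, or 152 devices. In the Placebo/LiRIS arm the 38 devices are half placebo and half active, so a count by arm alone does not show which content an early removal belongs to. These are planned numbers and do not measure bias.

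**The case against.** The strongest reply is that little is lost. SAP 10.2 already plans a summary and listing of the removal eCRFs by treatment period, and these may show every early removal with its reason. Lidocaine toxicity has its own table, which counts the signs whether or not the device was removed and is therefore broader than a removal count for that signal. Haematuria, retention and allergic reaction would be tabulated as adverse events by severity and causality. The triggers also overlap: a patient who is dizzy or bleeding may ask for removal, which places her in the table. The table is descriptive and bears on no hypothesis test.

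Most of this stands, and it rules out three stronger readings that a reader might infer.

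- *That removals for toxicity go unreported.* The documents do not support this. The events should be in the adverse event tables, and the removals may be in the eCRF summary and listing.
- *That most early removals are missed because six of seven triggers are unnamed.* The triggers are not mutually exclusive, and no frequencies are given.
- *That removal of an active Treatment 2 device will be shown against Placebo/Placebo.* That depends on a table layout not in the documents. The text leaves the placement open and does not establish an error.

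The reply does not supply a defined count of all early removals. The eCRF summary is described in terms of compliance with the procedures, its content cannot be confirmed, and the table dedicated to early removal is the one with the restricted definition.

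**Conclusion.** The point holds in a limited form. As worded, the SAP 10.2 table omits removals made solely on the investigator's decision under six of the seven protocol 5.6.3 triggers, and so undercounts early removals whenever such removals occur. No other defined output gives the full count, although SAP 10.0 treats completion of each device's cycle as relevant.

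The size is unknown. It could be zero if every affected patient also asks for removal, and any percentage would rest on assumed counts. The conclusion assumes that the table is programmed as the SAP words it and that the unseen eCRF summary is not itself a full count by cause. If that summary does give one, what remains is an inconsistency between two outputs in the same section. The matter is one of tolerability reporting. The primary analysis and the capture of safety data are unaffected.

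**What to change.** Reword the second paragraph of SAP 10.2 so that the table covers every IP out of the bladder before its scheduled removal, whatever the cause. For each, give the reason (expulsion, patient request, each other 5.6.3 trigger, device damage or other) and the days indwelling. Where a patient's request and a medical trigger coincide, record both. Present the table separately for the first Treatment 1 device, the second Treatment 1 device and the Treatment 2 device, by the actual content of that device, with the number inserted as denominator.

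The source is the existing insertion and removal eCRF data. Removal timing must already be available, because per-protocol membership depends on retention. That the reason for removal is also captured is an assumption to confirm against the form. The cost is one reworded paragraph and one revised descriptive table, with no additional patients and no change to any clinical rule.

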11.0 EFFICACY ANALYSES

The efficacy analyses will be primarily based on the mITT Population with selected tables being repeated using the PP population. Unless stated otherwise, baseline for efficacy is defined as the last non-missing efficacy assessment prior to first Treatment 1 IP insertion. All statistical tests will be 1-sided hypothesis tests performed at the 5% level of significance for main effects. All confidence intervals will be 2-sided 90% confidence intervals, unless stated otherwise.

11.1 **PRIMARY EFFICACY PARAMETER(S)**

The primary efficacy measure is the 7-day mean of the average daily bladder pain NRS (See Section 17.2.1 for definition of average daily bladder pain score).

The primary efficacy variable is the change from baseline to Week 4 Follow-Up post removal of the last IP in Treatment 1 period, using the 7-day mean of the average daily bladder pain NRS score. Patients are scheduled to have two IP insertion in Treatment 1 period and then a Week 4 Follow-Up visit. However, if a patients receives only one IP insertion in the study and has Week 4 Follow-Up assessment, it will be considered in the analysis.

The baseline 7-day mean daily average NRS score will be derived using the diary information from Day -7 to Day -1. In contrast, for patients that receive two IP insertion, the Week 4 Follow-Up mean 7-day average daily pain score will be derived from data collected from Day 50 to Day 56 from date of 1nd IP insertion or Day 36 to Day 42 for patients that receive just one insertion during Treatment 1 period. The mean baseline NRS will be derived if there are at least *any* 5 consecutive valid assessments within the 7-day assessment window (i.e., for baseline it would be day -7 to day -1). If the data that is available is for less than 5 consecutive days, as described above, then the value will be considered missing for that patient. Similarly, the Week 4 Follow-Up NRS will be derived if there are at least *any* 5 consecutive valid assessments within the 7-day assessment window (Day 50 to Day 56 for patients that received two insertion or Day 36 to Day 36 to Day 36 to Day 42 for patients that received just one IP in Treatment 1).

For the primary analysis, for patients that get two IP inserted during Treatment 1 period, the Week 4 Follow-up is counted from the 2nd IP removal time. In contrast, for patients that just received one IP before exiting the study, the Week 4 Follow-Up is counted from the IP removal date. Hence, for Treatment 1 period, Week 1 Follow-Up- Week 4 Follow-Up assessment are from last IP removal, whether or not a patient received one or two IPs.

For the primary analysis, for patients that have IP inserted, if there is no valid Week 4 Follow-Up NRS assessment and there is a valid Week 2 or 3 Follow-Up, weekly mean of the average daily bladder pain NRS, the Week 4 Follow-Up value will be imputed by the latest of the two values that is available (i.e., Week 2 or 3 Follow-Up). For the primary efficacy analysis, the null and the alternate hypothesis are as follows:

Null hypothesis: The mean change from baseline in average daily bladder pain NRS at Week 4 Follow-Up post IP removal is the same or worse for the treatment group that utilizes 2 consecutive LiRIS 400 mg compared to the treatment group that utilizes 2 consecutive LiRIS Placebo.

Alternative hypothesis: The mean change from baseline in average daily bladder pain NRS at Week 4 Follow-Up post IP removal is greater for the treatment group that utilizes 2 consecutive LiRIS 400 mg compared to the treatment group that utilizes 2 consecutive LiRIS Placebo.

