7.2.1 Primary Efficacy Variables

The primary efficacy variable is the change in average daily bladder pain NRS at Week 4 Follow-up Visit post removal of 2nd IP of Treatment 1 as compared to study baseline.

The average daily pain NRS of the preceding 7 days (at least 5 consecutive days) will be calculated and used to calculate baseline and change from baseline at each scheduled visit. If no data are available for at least a period of 5 consecutive days, that average will be considered missing for that patient. The primary timepoint is 4-week follow up after removal of the 2nd IP of Treatment 1. If there is no valid Week 4 Follow-up NRS assessment and there is a valid Week 2 or 3 Follow-up NRS assessment, the Week 4 Follow-up value will be imputed using the latest of the 2 values that is available (ie, Week 2 or 3 Follow-up).

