Table 17.2.1–1, presents for patients that receive more than one IP insertion, in days from first IP insertion within each treatment period the days to be included in each weekly summary. For patients that only receive one IP, Table 17.2.1-1 also presents in days from this IP insertion the days to be included in each weekly summary. For the postbaseline weeks that do not cover IP insertion or removal, a patient will be included in each weekly summary if they have at least 5 consecutive days of information within the summary week presented in Table 17.2.1-1. For the week intervals that cover IP insertion or removal a different rule is applied. For assessment weeks where there is IP insertion, the day of insertion and the two days after the day of insertion will not be included in the weekly average summary. The summary for such a week will be based on all available values, provided there are at least three days of daily assessments to be summarized (the days that are to be removed will be considered in the 5 day criteria). In contrast, for the week where IP removal occurs, the IP removal date and the day after the IP removal will be removed from the weekly average summary. The summary for such a week will be based on all available values provided there are at least three daily assessments to be summarized (the days that are to be removed will be considered in the 5 day criteria). The rational for excluding these IP insertion and removal dates is to reduce the impact of pain or pain medication that is related to the procedure rather than the disease under consideration.

Table 17.2.1–1 presents the weekly pain assessment windows.

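### SAP 11.1 names the primary endpoint as Week 4 after last IP removal but derives it from fixed days after insertion, so a patient whose last IP comes out early is scored on a later week.

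*SAP*

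**What the plan says.** **Definition.** SAP 11.1 gives the primary variable as the "change from baseline to Week 4 Follow-Up post removal of the last IP in Treatment 1 period", using the 7-day mean of the daily average pain NRS. It then says that the follow-up weeks up to and including "Week 4 Follow-Up assessment are from last IP removal, whether or not a patient received one or two IPs". Protocol 7.2.1 has the same anchor: "The primary timepoint is 4-week follow up after removal of the 2nd IP of Treatment 1".

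**Derivation.** For two IPs, SAP 11.1 says the Week 4 value "will be derived from data collected from Day 50 to Day 56 from date of 1nd IP insertion". For one IP the window is Day 36 to 42. The same section repeats these days in its validity rule, which needs at least 5 consecutive diary days inside the window. SAP 17.2.1 says that Table 17.2.1-1 "presents for patients that receive more than one IP insertion, in days from first IP insertion within each treatment period" the days that form each weekly mean, and for one-IP patients counts from that IP's insertion.

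**Protocol derivation.** Protocol 6.5.12 and 7.2.1 use the 7 days before the visit, not fixed study days.

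**Early removal or loss.** Protocol 5.6.3 provides for premature removal, including at the patient's request. Protocol 6.5.20 lists voiding of the IP as an IP event. SAP 10.2 plans a table of patients who lose the IP or ask for early removal, but gives no window rule for them. SAP 6.2 keeps every randomized patient with at least one insertion in the mITT population.

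**The concern.** The definition follows the removal date. The derivation follows the insertion date and changes only with the number of IPs inserted. SAP 11.1 gives no other days, so a programmer working from its numbers would use a fixed window even when the last IP came out early.

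At stake is what the primary value measures for those patients. The endpoint describes pain a set time after drug delivery stops; a shifted window describes a later time. The supporting analyses do not repair this. The no-imputation ANCOVA on the mITT population and the MMRM (SAP 11.1.1) use the same weekly windows. The per-protocol analysis requires the IPs to be retained for 28 days (SAP 6.4), so it drops these patients and leaves their primary value uncorrected. The groups are small: with 18 evaluable patients planned in the placebo group, one patient carries 1/18 = 5.6% of that group's unadjusted mean.

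**Working it through.** **Inputs**
- SAP study day = date − first insertion date + 1 (SAP 17.1), so SAP day = protocol day + 1.
- Scheduled last removal: protocol Day 28 with two IPs (Protocol 5.6.1), which is SAP Day 29. With one IP it is protocol Day 14, which is SAP Day 15.
- Windows: Day 50–56 (two IPs) and Day 36–42 (one IP), from SAP 11.1.

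**Which insertion the two-IP window counts from.** The ordinal in the SAP is mistyped. Counted from the second insertion (SAP Day 15), Day 50–56 would be SAP Day 64–70, or post-removal days 64−29 = 35 to 70−29 = 41, which is not Week 4. SAP 17.2.1 also says first insertion. So the count is from the first.

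**Reproducing the plan's windows, on schedule**
- Two IPs: 50−29 = 21 and 56−29 = 27.
- One IP: 36−15 = 21 and 42−15 = 27.

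Both give post-removal days 21–27, the seven days before a visit on post-removal day 28. The windows are correct for on-schedule removal.

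**Last removal or loss k days early**
- Two IPs: removal on SAP Day 29−k, so the window is 50−(29−k) = 21+k to 56−(29−k) = 27+k.
- One IP: removal on SAP Day 15−k, so the window is 36−(15−k) = 21+k to 42−(15−k) = 27+k.
- Days shared with 21–27: 7−k for k = 0 to 7, then 0.

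| k (days early) | Fixed window, post-removal days | Intended days shared |
|---|---|---|
| 0 | 21–27 | 7 |
| 1 | 22–28 | 6 |
| 2 | 23–29 | 5 |
| 3 | 24–30 | 4 |
| 5 | 26–32 | 2 |
| 7 | 28–34 | 0 |
| 13 | 34–40 | 0 |

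The last row is a second IP lost one day after insertion (protocol Day 15). A patient who received only one IP, removed on protocol Day 14, is scored on post-removal days 21–27. The two wore an IP for nearly the same time, but their windows start 34−21 = 13 days apart after removal. An early first removal does not matter if the last removal is on time.

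**Secondary point: Treatment 2.** SAP 10.0 says "A request for re-treatment can only be made 4-weeks after the second IP had been removed", and Protocol section 3 foresees insertion at the Week 4 visit. Assume two IPs, a Week 4 visit that moves with the early removal, and Treatment 2 inserted then. Insertion falls on SAP Day (29−k)+28 = 57−k. SAP 4.0 and 17.2 end the Treatment 1 period there, so 7−k days of Day 50–56 remain:
- k=2: insertion on Day 55, Days 50–54 remain (5 days), value valid.
- k=3: insertion on Day 54, Days 50–53 remain (4 days), value missing under the 5-consecutive-day rule and imputed from Week 3 or Week 2.

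At k=3 the intended days are SAP Day 47–53 (removal on Day 26, plus 21 to 27). All seven precede insertion, so the intended diary week may be complete while the value is imputed.

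If Week 3 is Day 43–49 (an assumption, since the table body is not visible), the imputed value covers post-removal days 14+k to 20+k:
- k=3: days 17–23, 3 intended days shared.
- k=5: days 19–25, 5 shared.
- k=7: days 21–27, all 7 shared.

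**The case against.** **The SAP states the right anchor.** SAP 11.1 says more than once that the follow-up weeks count from last removal, and its day numbers can be read as the on-schedule translation of that rule. Table 17.2.1-1 might settle the matter, and its body is not visible. This stands in part: the wrong week follows only if the stated days are programmed. But those are the only days SAP 11.1 gives, it repeats them in the validity rule, and SAP 17.2.1 describes the table as counted from insertion.

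**Small shifts matter little.** At k=1 and k=2, 6 and 5 of the 7 days are still right. This stands; only from k=7 is the week wholly different.

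**Open-label days in the primary value.** A reader might infer that, after an early removal, days on open-label LiRIS enter the primary mean. The documents do not support this. SAP 4.0 ends the double-blind period at the last assessment before Treatment 2 insertion, SAP 17.2 ends Treatment 1 at that insertion, and SAP 17.2.1 sets its windows within each treatment period. The natural reading is that such days belong to Treatment 2.

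**The Treatment 2 overlap is conditional.** SAP 10.0 sets an earliest time for a request, not a schedule. Protocol 5.6.2 and 5.8.2 tie retreatment to the Week 4 visit, and whether that visit moves after an early removal depends on a schedule that is not visible. Protocol 5.6.2 also lets insertion follow qualification by up to 14 days. On the assumed Week 3, the imputed value recovers some or all of the intended days. This stands, so the overlap is secondary.

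**Conclusion.** The concern holds for the derivation window. SAP 11.1 contains two rules for the primary value that agree only when the last Treatment 1 IP leaves on schedule. With removal or loss k days early, the stated days give post-removal days 21+k to 27+k and share 7−k of the seven intended days, none from k=7. This rests on the stated windows being programmed as written. The Treatment 2 consequence rests further on the Week 4 visit moving with removal and on insertion at that visit.

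The documents do not say how many patients would be affected, so the effect on the result cannot be computed. A reader might infer a bias toward one group or a loss of power; neither follows. No direction is claimed, and the planned 36 versus 18 evaluable patients and the stated 76% power are unchanged. The point is limited to early removal or loss. It should be settled before database lock, because it decides which diary days form the primary value.

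**What to change.** Before database lock, in SAP 11.1 and Table 17.2.1-1:
- Anchor Follow-Up Weeks 1–4 to the actual date of last Treatment 1 IP removal, or of recorded loss, with Week 4 = post-removal days 21–27.
- State that Day 50–56 and Day 36–42 are only the on-schedule equivalents.
- Confirm, consistent with SAP 4.0 and 17.2, that no diary day on or after Treatment 2 insertion is used.
- Keep the 5-consecutive-day rule.
- Reconcile the window with the protocol's rule of the 7 days before the visit (6.5.12, 7.2.1), and list any remaining departure in SAP 18.0. The two changes now listed there do not concern this window.

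The cost is SAP wording and a small programming change. The removal date is already needed, because SAP 17.2.1 says that in a removal week "the IP removal date and the day after the IP removal will be removed from the weekly average summary". Patients whose last removal is on schedule, with no Treatment 2 before post-removal day 28, keep the same seven days.
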